3.1.2.1 Cohort 1, Phase IA, Arm 1A

6 to 12 patients will be enrolled into Arm 1A.

Dose de-escalation will proceed in dose levels of 6 patients.

6 subjects will be enrolled in Dose Level 0 (**Table 5**). Patients will be treated with M7824 starting on Day -14 plus M9241 starting on Day 1 of Cycle 1.

If < 2 patients experience a DLT during DLT period, DL 0 will be used as recommended Phase IB dose for Arm 1B.

If ≥ 2 patients experience a DLT during DLT period at DL 0, the DL 0 enrollment will be stopped.

The next 6 subjects will be enrolled into Dose Level -1. If < 2 patients experience DLT during DLT period, this dose DL -1 will be used as recommended Phase IB dose for Arm 1B.

If ≥ 2 patients experience a DLT at DL -1, the enrollment will be stopped and no further attempts at completing the safety run-in of M7824 in combination with M9241 will be conducted and Arm 1B and phase II expansion cohort of M7824 and M9241 in combination with SBRT will not be carried out.

Table 5: Dose Levels of M7824 and M9241 in Arm 1A

Dose level	M7824, mg, IV every 2 weeks	M9241, $\mu\text{g}/\text{kg}$, SQ, every 4 weeks
DL 0	1,200	16.8
DL -1	1,200	12.0

3.1.2.2 Cohort 2, Phase IB, Arm 1B

6 to 12 patients will be enrolled in Arm 1B. Enrollment will start after completion of Arm 1A.

Dose de-escalation will proceed in dose levels of 6 patients.

6 subjects will be enrolled in Dose Level 0 (**Table 6**) and treated with combination of M7824, M9241 and SBRT.

If < 2 patients experience DLT during DLT period, the Dose level 0 will be the RP2D and next patients will be enrolled into Cohort 3 the phase II portion of the study.

If ≥ 2 experience a DLT at DL 0, the Dose Level 0 enrollment will be stopped, and DL -1 will be tested in 6 patients. If <2 patients experience a DLT, dose level -1 will be used as RP2D for M7824 and M9241 in combination with SBRT in the Phase II.

If ≥ 2 patients experience a DLT at DL -1, the dose Level -1 enrollment will be stopped and no further attempts at completing the Arm 1B of M7824 and M9241 in combination with SBRT will be conducted and Arm 2B and phase II expansion cohort of M7824 and M9241 in combination with SBRT will not be carried out.

Table 6: Dose Levels of M7824 and M9241 in combination with SBRT in Arm 1B.

Dose level	M7824, mg, IV every 2 weeks	M9241, µg/kg, SQ, every 4 weeks	SBRT
DL 0	1,200	MTD of M9241 estimated during Phase IA (16.8 or 12)	5 x 5 Gy
DL -1	1,200	If MTD estimated during Phase IA is 16.8 then 12.0	5 x 5 Gy
		If MTD estimated during Phase IA is 12.0, then 8.0	

3.1.3 Phase II, Cohort 3, Arm 2

The efficacy part of the study will be conducted with the M7824 and M9241 dose level found to be safe in combination with SBRT during phase IB. Once a recommended phase 2 dose of M7824 and M9241 has been determined, up to 25 subjects will be evaluated at that dose level, inclusive of those patients treated at the RP2D during the safety run-in.

Enrollment will start when RP2D is estimated and 28 days of observation after first treatment of 6th subject at RP2D in Arm 1B have passed.

During first stage of Phase II 16 patients will be enrolled. If 0 to 1 of 16 patients respond (PR or CR as defined in Section 6.3), then no further patients will be enrolled. If 2 or more of the first 16 evaluable patients enrolled have a response (PR or CR), then during second stage accrual will continue until a total of 25 evaluable patients have been enrolled.

3.2 STUDY STOPPING RULES

For safety reasons, the enrollment will be temporarily halted until an expedited safety report has been evaluated by the investigators, IND sponsor, and submitted to the FDA for either of the following events attributable to treatment regimen occurring within 28 days of receiving investigational agent (s):

- One occurrence of grade 5 toxicity, attributable to treatment regimen.
- Two occurrences of grade 4 toxicity, attributable to treatment regimen.

3.3 DRUG ADMINISTRATION

3.3.1 M7824

M7824 will be administered as a 1-hour (-10 minutes / +20 minutes) IV infusion on Days 1 and 15 of every cycle, starting Cycle 1. In Phase IA there is additional infusion 14 days before Day 1 of Cycle 1.

On the days of combined M7824 and M9241 treatment M7824 will be infused at least 30 minutes after M9241 injection.

M7824 will be administered as an intravenous (IV) infusion via a peripheral OR central vascular access device (VAD) if patient has VAD already installed. Confirm patient has a titanium port before accessing the Central VAD. A 0.2-micron polyethersulfone (PES) in-line filter is mandatory for administration.

Current experience revealed that infusion related reactions (IRRs) to M7824 seldom occur and are generally mild to moderate in severity. Therefore, administration of a premedication is generally not required.

If an Investigator deems it necessary to administer a premedication to a particular participant, an antihistamine (for example, 25-50 mg diphenhydramine) and acetaminophen 500-650 mg intravenously or equivalent oral dose is recommended approximately 30 to 60 minutes prior to each dose of M7824. If Grade ≥ 2 infusion reactions are seen during the first two infusions, premedication should not be stopped. Steroids as premedication are not permitted.

Hypersensitivity reactions may require immediate intensive care. M7824 should be administered in a setting that allows for immediate access to an intensive care unit or equivalent environment and administration of therapy for anaphylaxis, such as the ability to implement immediate resuscitation measures. Steroids (dexamethasone 10 mg), epinephrine (1: 1,000 dilution), allergy medications (IV antihistamines), bronchodilators, or equivalents, and oxygen should be available for immediate access.

A complete guideline for the emergency treatment of anaphylactic reactions according to the Working Group of the Resuscitation Council United Kingdom and can be found at <https://www.resus.org.uk/pages/reaction.pdf>

For prophylaxis of flu like symptoms, a nonsteroidal anti-inflammatory drug (NSAID), e.g., ibuprofen 400 mg or comparable NSAID dose, may be administered 2 hours before and 8 hours after the start of each IV infusion.

Patients must be observed for 2 hours after the first M7824 dose. If no reactions are observed, the patients need to be monitored for only 30 minutes after subsequent doses.

If an allergic reaction occurs, the subject must be treated according to the best available medical practice. Please see the guidelines for handling of infusion-related reaction in **Table 8**.

Investigators should also monitor subjects closely for potential irAEs, which may become manifest after several weeks of treatment. Such events may consist of persistent rash, diarrhea and colitis, autoimmune hepatitis, arthritis, glomerulonephritis, cardiomyopathy, or uveitis and other inflammatory eye conditions.

Vital signs must be measured within 30 minutes before and 30 minutes following M7824 infusions.

3.3.2 M9241

M9241 will be administered as a subcutaneous injection on Day 1 of every cycle.

M9241 will be injected at least 30 minutes before M7824 infusion.

3.3.3 SBRT

Radiation therapy will be starting on Day 17 (+5 days) of Cycle 1 and continue for 5 consecutive business days (except federal holidays).

A summary of the SBRT schedule in combination with M7824 and M9241 is shown in **Schema 2**.

3.4 DOSE MODIFICATIONS:

In case of toxicity as defined below, definitely attributed to one of the study drugs and/or SBRT, patient may be taken off this drug and/or SBRT and per PI discretion may continue treatment with another drug only or drug combined with SBRT.

When, at the beginning of a treatment cycle, treatment delay related to M7824 is indicated, per PI discretion treatment with M9241 and or SBRT might not be delayed.

If, in the opinion of the investigator, a toxicity is considered to be due solely to one drug, the dose of another drug does not require modification.

3.4.1 M7824

Treatment modifications for reactions caused by M7824 are addressed in [Table 7](#), [Table 8](#), [Table 9](#), [Table 10](#), [Table 11](#), and [Table 12](#).

Table 7: Treatment Modification Guidance for Symptoms of Infusion-Related Reactions including Immediate Hypersensitivity.

NCI-CTCAE Grade	Treatment Modification for M7824
Grade 1 – mild Mild transient reaction; in general, infusion interruption not indicated; intervention not indicated.	
• Increase monitoring of vital signs as medically indicated as participants are deemed medically stable by the attending Investigator.• Hold infusion if deemed necessary by the investigator.
Grade 2 – moderate Therapy or infusion interruption indicated but responds promptly to symptomatic treatment (for example, antihistamines, nonsteroidal anti-inflammatory drugs, narcotics, IV fluids); prophylactic medications indicated for ≤ 24 h.	
• Stop the infusion of the study intervention.• Increase monitoring of vital signs as medically indicated as participants are deemed medically stable by the attending Investigator.• If symptoms resolve quickly, resume infusion at 50% of original rate with close monitoring of any worsening signs and symptoms, otherwise dosing held until resolution of symptoms with mandated premedication for the next scheduled visit.• If not improving, consider administration of glucocorticoids and stop the infusion for that day.• If the participant has a second IRR Grade ≥ 2 on the slower infusion rate despite premedication, the infusion should be stopped, and the investigator may consider withdrawal of this participant from the study.

NCI-CTCAE Grade	Treatment Modification for M7824

Grade 3 or Grade 4 – severe or life-threatening
 
Grade 3: Prolonged (for example, not rapidly responsive to symptomatic medication and/or brief interruption of infusion); recurrence of symptoms following initial improvement; hospitalization indicated for clinical sequelae.
 
Grade 4: Life-threatening consequences; urgent intervention indicated.
	
 • Stop the infusion of study intervention immediately and disconnect infusion tubing from the participant with additional appropriate medical measures and closely monitor until deemed medically stable by the attending Investigator. Hospitalization and/or close monitoring is recommended • Administration of glucocorticoids may be required • For Grade 3 or 4 IRRs, permanent discontinuation of study intervention is mandated

Once the infusion is interrupted or rate reduced to 50% of previous infusion rate, it must remain decreased for all subsequent infusions.
 
For all types and grades of infusion reactions, details about drug physical constitution, method of preparation, and infusion must be recorded.
 
Participants should be instructed to report any delayed reaction immediately.
	

Once the infusion is interrupted or rate reduced to 50% of previous infusion rate, it must remain decreased for all subsequent infusions.
 
For all types and grades of infusion reactions, details about drug physical constitution, method of preparation, and infusion must be recorded.
 
Participants should be instructed to report any delayed reaction immediately.
	

Table 8: Management of immune-mediated adverse events

Immune-related AEs are specific to immunotherapies and vary by organ system. The following immune-related AEs are important identified risks for M7824:
 
 • Immune-related pneumonitis • Immune-related hepatitis • Immune-related colitis • Immune-related nephritis and renal dysfunction • Immune-related endocrinopathies • (thyroid disorders, adrenal insufficiency, type 1 diabetes mellitus, pituitary disorders) • Immune related rash • Other immune-related events (myositis, myocarditis, encephalitis) 
The following immune-related AEs are important potential risks for M7824:

--

- Guillain-Barré syndrome
- Uveitis
- Pancreatitis
- Myasthenia gravis/myasthenic syndrome

Recommended guidance and management for specific irAEs are provided in the current National Comprehensive Cancer Network (NCCN) guideline available at <http://www.nccn.org>.

Requirements in addition to NCCN guidelines:

- Permanent treatment discontinuation is required in case of immune-related Grade 4 rash/inflammatory dermatitis, nephritis, autoimmune hemolytic anemia, hemolytic uremic syndrome, aplastic anemia, immune thrombocytopenia, acquired thrombotic thrombocytopenic purpura inflammatory arthritis, myositis and polymyalgia-like syndrome.
- For Grade 4 immune-related lymphopenia, permanent treatment discontinuation will be required, if lymphopenia is considered immune-related in nature, no clear alternative explanation exists for the event, and it does not resolve within 14 days. Permanent treatment discontinuation is not required when the AE is manifested by a single laboratory value out of normal range without any clinical correlates. In this case, treatment should be held until the etiology is determined. If the event is not considered immune-related and resolves to Grade ≤ 1 , restarting treatment may be considered.
- For Grade 1 immune-related pneumonitis: continue treatment. If clinically indicated, monitor participants weekly or more frequently as needed with history, physical examination and pulse oximetry. If symptoms appear and/or changes in the physical exam are noted, treat as Grade 2.
- For myositis: in case of management with rituximab, treatment should be discontinued.
- For Grade 3 or 4 endocrinopathies: withhold until clinically stable or permanently discontinue depending on severity.
- For hepatitis with no tumor involvement of the liver: withhold if total bilirubin increases to more than 1.5 and up to 3 times ULN, permanently discontinue if more than 3 times ULN
- Hepatitis with tumor involvement of the liver: permanently discontinue if total bilirubin increases to more than 3 times ULN.

Table 9: Management of M7824 mediated Skin Reactions

- Hyperkeratosis
- Keratoacanthoma
- Cutaneous squamous cell carcinoma (cSCC)
- Basal cell carcinoma
- Actinic keratosis

Management

• Discontinuation or termination not required in most cases. Continuation of treatment should be evaluated by the Investigator.• Emollients may be used• Develop diagnostic and treatment plan in collaboration with Investigator and dermatologist• Treatment follow-up will depend on number and localization of lesions.
○ Single lesion: full excision may be recommended○ Multiple lesion or location not suitable for full excision: Mohrs surgery, cryotherapy or other standard treatment options depending on pathology. Retinoids may be used per Investigator decision.• Close clinical follow-up for re-evaluation, resolution and potential recurrence should be implemented• In general, treatment of M7824 mediated skin lesions should be based on local guidelines/standard of care.
Additional consideration: Keratoacanthoma lesions may resolve spontaneously without surgical intervention within weeks after discontinuing bintrafusp alfa.
Consult with Medical Monitor as needed for management of M7824 mediated skin lesions.

Table 10: Management of Treatment-Related Anemia

• All relevant hematological testing for treatment-related anemias should be done prior to a blood transfusion, if clinically feasible
Basic Anemia Evaluation

• CBC with emphasis on red cell indices• If indicated and at clinical discretion, the following should be considered:
○ Iron studies○ Serum Folate and Vit B12 values○ Coagulation factors○ Fecal occult blood○ Urinalysis○ Hormone panel: TSH, Erythropoietin○ Peripheral blood smear
Further recommendation based on suspected etiology (in addition to basic anemia testing)

 • Suspected Hemolysis 
 ○ bilirubin, LDH, Coombs test, haptoglobin • Suspected bleeding: 
 ○ Consider imaging/interventional radiology consultation as indicated ○ Consider imaging and/or endoscopy as clinically indicated • Suspected aplastic anemia: 
 ○ Hematology consultation ○ Consider bone marrow aspiration/morphologic evaluation

Additional consideration: In general, blood transfusions and erythroid growth factors are permitted as clinically indicated.

Table 11: Management of Bleeding Adverse Events

Bleeding Adverse Events	

 • Bleeding adverse events are considered an important identified risk for M7824. • In general, mild and moderate mucosal bleedings resolve without discontinuation of treatment. • These events may include, but are not limited to the following: 
 ○ Epistaxis ○ Hemoptysis ○ Gingival bleeding ○ Hematuria 	
Non-tumor Bleeding	
Grading	Management
Grade 2	
 • If resolves to Grade ≤ 1 by the day before the next infusion, study intervention may be continued. • If not resolved to Grade ≤ 1 by the day before the next infusion, but is manageable and /or not clinically relevant, consult Medical Monitor to assess if clinically reasonable to administer the following infusion.
Grade 3	
 • Permanently discontinue treatment unless an alternative explanation can be identified (such as concomitant use of antithrombotic agents, traumatic events, etc.) • In case of alternative explanations, hold study treatment until the event recovers to Grade ≤ 1

Grade 4	
 Treatment must be permanently discontinued if no alternative explanation is identified.
Tumor Bleeding	
Grade \geq 2	
 Study treatment must be held till the event recovers to Grade \leq 1 Permanently discontinue treatment if the Investigator considers the participant to be at risk for additional severe bleeding.

Table 12: Impaired Wound Healing

 Impaired wound healing is considered important potential risk for M7824 Management should be discussed with Medical Monitor for participants requiring surgery on study. It is recommended to hold study intervention for approximately 4 weeks post major surgery for observation. Post-operative wound healing should be closely monitored

3.4.2 M9241

Modifications of M9241 are explained in [Table 14](#)

After Dose level -1, no more dose reduction is allowed, and patient will be taken off M9241 treatment.

Table 13: M9241 Dose Reduction Levels:

Dose Level (DL)	Agent Dose
0	16.8 μ g/kg (or 12.0 μ g/kg) every 4 weeks
-1	12.0 μ g/kg (or 8.0 μ g/kg) every 4 weeks

Table 14: M9241 Dose Modification Instructions

(CTCAEv5) Grade	Action
Non-hematological, Grade 1 or 2	Continue M9241 therapy at full dose prescribed. Apply maximum supportive care recommendations. If prolonged duration of Grade 2 adverse event (\geq 7 days) is affecting quality of life, decrease dose to DL -1, if symptoms persist and continue

(CTCAEv5) Grade	Action
	to affect quality of life for ≥ 7 more days, permanently discontinue M9241.
Non-hematological, Grade 3 or 4 (excluding cardiac, hepatobiliary events, interstitial pneumonitis or Grade 4 inflammatory response syndrome)	Apply maximum supportive care recommendations. Hold M9241 therapy until recovery to Grade ≤ 1 (up to 14 days). If non-hematological, symptomatic Grade 3 or 4 adverse events NOT resolved to Grade ≤ 1 within 14 days, discontinue M9241. If recurrence of adverse event after drug hold/ interruptions is observed, and maximum supportive care measures applied, hold drug once again until recovery to Grade ≤ 1 (up to 14 days) and restart drug at DL-1. If adverse event recurs, M9241 must be permanently discontinued.
Grade 3 or 4 interstitial pneumonitis or Grade 4 inflammatory response syndrome	M9241 must be permanently discontinued
Cardiac Adverse Events	
Cardiac (Severity corresponding to NYHA criteria)	M9241 therapy to be discontinued permanently in case of symptomatic NYHA class III and IV CHF. M9241 therapy to be held, continued, or resumed accordingly for patients with NYHA class I or II CHF.
Hepatobiliary Adverse Events	
Grade 2 AST/ALT	Hold M9241 for 2 weeks and restart drug at next scheduled dose at DL 0 (full dose) if events resolved to \leq Grade 1. If adverse events NOT resolved to Grade ≤ 1 within 2 weeks, restart M9241 at DL-1.
Grade 3 and 4 AST/ALT* and Grade ≥ 2 total bilirubin elevation	Hold M9241 for 2 weeks; restart drug at next scheduled dose at DL-1 if events resolved to \leq Grade 1. If adverse events NOT resolved to Grade ≤ 1 within 2 weeks, discontinue M9241 If Grade 3 AST/ALT or Grade 2 total bilirubin events recur after dose reduction to DL-1, then discontinue M9241.
Hematological, Grade 1 or 2	No modification required
Grade 3 or 4 thrombocytopenia associated with bleeding	M9241 must be permanently discontinued

(CTCAEv5) Grade	Action
event which does not result in hemodynamic instability but requires an elective platelet transfusion, or a life-threatening bleeding event which results in urgent intervention and admission to an Intensive Care Unit	
Grade 4 hematologic toxicity lasting ≥ 7 days despite of medical intervention (Note: Grade 4 neutropenia lasting >5 days)	M9241 must be permanently discontinued
Cytokine release syndrome	M9241 must be permanently discontinued
* retest within 3 days from the first occurrence and then weekly to determine if ALT elevation persists	

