1.2.6 M9241

M9241 was evaluated in a phase I study on safety, tolerability, pharmacokinetics, biological and clinical activity, as well as the effects on immune cell subsets and TCR clonality in patients with metastatic or locally advanced solid epithelial or mesenchymal tumors at the National Institute of Health (NIH) Clinical Center.[48]

A total of 59 patients were enrolled and treated with M9241. The single ascending dose cohort included a total of 22 patients who received one single dose administration of M9241 on day 1 and completed the study after 28 days of safety observation. In the multiple ascending dose escalation and expansion cohorts, a total of 37 patients were enrolled and treated every four weeks.

The primary objective of this trial was to determine the MTD as defined by the number of DLTs. None of the subjects treated with single or multiple doses up to and including 12.0 µg/kg experienced a DLT. At the 16.8 µg/kg dose level, one out of six subjects had a DLT (Grade 3 increase in ALT). At the 21.8 µg/kg dose level, two out of six subjects had a DLT (Grade 3 increase in AST and ALT; Grade 3 increase in lipase without clinical signs of a pancreatitis) and the MTD was determined to be 16.8 µg/kg administered subcutaneously every four weeks, per formal protocol criteria.

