1.2.6.1 Treatment-related adverse events

The most frequently observed treatment-related adverse event was a decrease in lymphocyte count in 27 subjects (45.8%), followed by a decrease in WBCs in 24 subjects (40.7%), fever and an increase in AST, each in 21 subjects (35.6%), an increase in ALT in 20 subjects (33.9%), and anemia and flu-like symptoms, each in 18 subjects (30.5%) (**Table 1**).

Twelve of the overall 59 subjects (20.3%) experienced at least one ≥ Grade 3 treatment-related adverse event. These included events of a decrease in lymphocyte count in five subjects (8.5%), a decrease in neutrophil count in four subjects (6.8%), an increase in ALT in three subjects (5.1%), a decrease in WBCs in two subjects (3.4%), and hypokalemia, hyperhidrosis, an increase in alkaline phosphatase, an increase in AST, and an increase in lipase, each in one patient (1.7%). Of these subjects who had Grade ≥ 3 treatment-related AEs, all were transient and only one event (Grade 3 hyperhidrosis) was symptomatic. Only one Grade 4 event (asymptomatic decrease in lymphocyte count) was observed and no Grade 5 treatment-related AE was observed.

Table 1: Adverse Events of M9241

	Grade 1/2 n (%)	Grade 3 n (%)	Grade 4 n (%)
Decrease in lymphocyte count	21 (35.6%)	5 (8.5%)	1 (1.7%)
Decrease in neutrophil count	6 (10.2%)	4 (6.8%)	0
Thrombocytopenia	12 (20.3%)	0	0
Decrease in WBCs	22 (37.3%)	2 (3.4%)	0
Hyperglycemia	10 (16.9%)	0	0

	Grade 1/2 n (%)	Grade 3 n (%)	Grade 4 n (%)
Hypoalbuminemia	6 (10.2%)	0	0
Hypokalemia	0	1 (1.7%)	0
Hypophosphatemia	6 (10.2%)	0	0
Hyperhidrosis	0	1 (1.7%)	0
Anemia	18 (30.5%)	0	0
Fatigue	10 (16.9%)	0	0
Fever	21 (35.6%)	0	0
Flu-like symptoms	18 (30.5%)	0	0
Increase in ALT	17 (28.8%)	3 (5.1%)	0
Increase in alkaline phosphatase	12 (20.3%)	1 (1.7%)	0
Increase in AST	20 (33.9%)	1 (1.7%)	0
Increase in lipase	0	1 (1.7%)	0

Nine subjects (15.5%) experienced serious AEs, two of which (3.4%) were assessed as related to M9241 treatment. Generally, similar incidences of AEs and serious AEs were observed between the single dose and multiple dose groups despite different observation periods. In the latter, the rate of AEs \geq Grade 3 and AEs related to M9241 was slightly higher. In the single dose group, no subject experienced an AE leading to permanent discontinuation of treatment and no subject had any serious AEs assessed as related to M9241 (**Table 1**).

Table 2 below summarizes Treatment Emergent Adverse Events of M9241 from phase I clinical testing.

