1.2.9 Rationale for this clinical trial

The administration of M7824 and M9241 in combination with SBRT to subjects with locally advanced pancreatic cancer is justified by the following:

- The synergistic action of PD-L1 inhibition mediated by the dual PD-L1 TGFβ blocker M7824 and RT, including the emerging clinical data of improved outcome upon checkpoint blockade and RT.
- The synergistic action of M9241 and RT.
- The synergistic action of M7824 and M9241.

- Administered dose and schedule of the standard RT is not changed due to the addition of M7824 and/or M9241.
- M7824 and M9241 and RT have largely non-overlapping toxicity profiles which are manageable.

1.2.9.1 Rationale for M7824 and M9241 Dose Levels with special consideration of overlapping toxicities with SBRT

The safety run-in of M7824 and M9241 will be carried out in patients with stages III and IV or locally advanced pancreas cancer.

The toxicity profile of M7824 is predominantly benign, see section [1.2.5](#).

M7824 and SBRT carry hematological toxicities (anemia for M7824), M9241 and SBRT harbor overlaps in hematological and non-hematological GI toxicities in the form of lymphopenia as well as LFT elevations (although they were for M9241 reported as clinically not significant). While these AEs for monotherapy with M7824 and M9241 appear to be manageable and not life-threatening (predominantly grade 1 and 2 for M9241) it is not known what the side effect profile is in combination with SBRT. Thus, there is a dedicated safety run-in cohort to determine safety and tolerability of M7824 and M9241 when combined with SBRT (Phase IB part of the study).

The first 6 patients will receive M7824 at a fixed dose of 1,200 mg on day -14 followed by M7824 +M9241 combination on cycle 1 day 1.

The rationale for the starting dose of 16.8µg/kg of M9241 via subcutaneous injection every 4 weeks, which was found to be the MTD of this agent, is based on the clinical safety data of this dose in the phase I study of 59 patients conducted at the Center for Cancer Research NIH.[\[48\]](#)

Due to the transient clinically mild nature of these AEs (see section [1.2.6.1](#)) M9241 is initially combined at its MTD of 16.8µg/kg every 4 weeks dose with M7824.

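### Read literally, the Grade 2 AST/ALT row of Table 14 sends a patient already reduced to DL -1 back to full-dose M9241

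*Combined protocol and SAP*

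**What the plan says.** Table 13 (section 3.4.2) lists two M9241 levels for dose reduction: DL 0 is 16.8 (or 12.0) µg/kg and DL -1 is 12.0 (or 8.0) µg/kg, each every 4 weeks.

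Table 14 gives the actions by event. For Grade 2 AST/ALT it says: "Hold M9241 for 2 weeks and restart drug at next scheduled dose at DL 0 (full dose", provided the event has come down to Grade 1 or lower. If it has not, the instruction is: "within 2 weeks, restart M9241 at DL-1".

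The next row covers Grade 3 and 4 AST/ALT and bilirubin of Grade 2 or higher. Once resolved, these restart at DL -1, and the row adds: "If Grade 3 AST/ALT or Grade 2 total bilirubin events recur after dose reduction to DL-1, then discontinue M9241". The first row of the table also leads to DL -1 for prolonged Grade 2 non-hematological events that affect quality of life: "decrease dose to DL -1, if symptoms persist and continue".

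The only general limit in 3.4.2 is a floor: "After Dose level -1, no more dose reduction is allowed, and patient will be taken off M9241 treatment".

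**The concern.** The Grade 2 AST/ALT row fixes a destination (DL 0) rather than a change relative to the current dose. That is harmless for a patient still on the DL 0 dose. For a patient already at DL -1 it turns a new hepatic event into an instruction to increase the dose.

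The toxicity involved is one the protocol itself watches. At 16.8 µg/kg in the first M9241 trial, "one out of six subjects had a DLT (Grade 3 increase in ALT") (section 1.2.6). Section 1.2.9.1 expects overlap with radiotherapy: "M9241 and SBRT harbor overlaps in hematological and non-hematological GI toxicities in the form of lymphopenia as well as LFT elevations", and says that the side-effect profile of the combination with SBRT is not known. Section 3.1.2 also lets a patient who has had a DLT continue with dose reductions under 3.4, so the reduction that is undone could be one made because of a DLT.

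At stake is the dose given to individual patients. An investigator who sensibly kept the reduced dose would be departing from the written rule.

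**Working it through.** **Step 1. Who can be at DL -1 and still on M9241?** Table 14 gives four routes:

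1. Grade 3-4 AST/ALT, or bilirubin of Grade 2 or higher, resolved within 2 weeks.
2. Grade 2 AST/ALT not resolved within 2 weeks.
3. Prolonged Grade 2 non-hematological events affecting quality of life.
4. Recurrent Grade 3-4 non-hematological events.

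None of these needs a dose level to close, so the situation can arise in any cohort.

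**Step 2. Which rule then applies to a later Grade 2 AST/ALT rise?** The discontinuation rule in the neighbouring row names Grade 3 AST/ALT and Grade 2 bilirubin, not Grade 2 AST/ALT. The floor rule limits further reductions, and a restart at DL 0 is not a reduction. The Grade 2 AST/ALT row is what remains.

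**Step 3. Result for each current dose, event resolved.**

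| Patient | Dose before hold | Dose after restart as written | Change |
|---|---|---|---|
| On DL 0 | 16.8 or 12.0 | same | none |
| DL 0 = 16.8, reduced | 12.0 | 16.8 | 16.8/12.0 = 1.40, +40% |
| DL 0 = 12.0, reduced | 8.0 | 12.0 | 12.0/8.0 = 1.50, +50% |
| Assigned 8.0 from the start | 8.0 | not defined | ambiguous |

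For the two reduced patients, the same event left unresolved gives a restart at DL -1. The better outcome raises the dose and the worse one does not.

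**Step 4. How many patients?** The documents give no rate for the full sequence, so this is illustrative. It counts only the Grade 3 ALT route to DL -1.

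- Grade 3 ALT on M9241 alone (section 1.2.6.1, Table 1): 3/59 = 5.1%, exact 95% interval 1.1% to 14.1%. Times 25: 1.3 patients reduced (0.3 to 3.5).
- Assume that 10% to 50% of those reduced later have a Grade 2 rise that resolves (this fraction is not in the documents): 1.27 × 0.10 = 0.13 and 1.27 × 0.50 = 0.64 of 25.
- If all three events fell among the 37 multiple-dose patients (not stated): 3/37 = 8.1%, or 2.0 of 25, giving 0.2 to 1.0.
- Using the single DLT at 16.8 µg/kg: 1/6, or 4.2 of 25, giving 0.4 to 2.1. The exact interval on 1/6 is 0.4% to 64%, so this shows only how little is known.

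The 59 include 22 single-dose patients and other dose levels. One of the two DLTs at 21.8 µg/kg was a Grade 3 AST and ALT rise (section 1.2.6), at a dose above any used here, which pulls the figure down for this trial. The other three routes, and the effect of M7824 and SBRT, are not counted, which pulls it up.

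**Step 5. How likely is an assigned dose of 8.0 µg/kg?** Under Table 6 it opens only if 16.8 fails and 12.0 passes in Phase IA, and 12.0 then fails in Phase IB. Let c be the probability of at least 2 DLTs in 6 patients. With an assumed DLT rate of 10%, 20% or 30% at every level, c = 0.114, 0.345, 0.580. Then 8.0 opens with probability c²(1−c) = 0.012, 0.078, 0.141, and becomes the RP2D with probability c²(1−c)² = 0.010, 0.051, 0.059.

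**The case against.** The strongest defence is that the row was written for a first event in a patient still at DL 0: same dose if it resolves, one step down if it does not. The pairing of DL 0 with DL -1 inside one cell fits that, and it is probably what was meant. But the restriction is not written, and other rows of the same table keep patients on drug at DL -1. Reading the words in brackets as the patient's own starting dose does not help either, because a reduced patient still goes back up.

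The clinical consequence can also be called modest, and this largely stands. The patient returns to a dose once assigned to them. In Phase II at DL 0 that dose has had fewer than 2 DLTs in 6 patients with SBRT. The event must have resolved first. In the earlier trial the treatment-related events of Grade 3 or higher were mild in course: "all were transient and only one event (Grade 3 hyperhidrosis) was symptomatic" (section 1.2.6.1). Section 1.2.9.1 reports the LFT elevations on M9241 as not clinically significant, and the team discusses each patient weekly (section 7.4.1). These points limit the harm; they do not correct the rule.

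A reader might go further and infer that a patient who starts at 8.0 µg/kg is instructed to go up to 12.0, the level just closed in Arm 1B. The documents do not support that as a written instruction. Table 13 lists 8.0 only as a reduced level, so this patient has no DL 0 entry, and the phrase in brackets can mean the assigned dose. Similarly, a patient assigned 12.0 is covered by the bracketed 12.0 in the DL 0 line. Both cases are gaps or ambiguities, and step 5 shows that the 8.0 case is uncommon under the assumed rates.

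**Conclusion.** Wrong as written (minor, patient safety). Followed literally, the Grade 2 AST/ALT row returns an already reduced patient to full dose, +40% or +50%, when a further hepatic event resolves. This rests on the text of Tables 13 and 14 and on the absence of any no-re-escalation rule for M9241. It does not depend on the patient counts.

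The likely number affected is small: about 0.1 to 0.6 of 25 Phase II patients at the 3/59 rate, on an assumed recurrence fraction of 10% to 50%. Larger figures need the 1/6 rate, which rests on one event. It would be wrong to infer that a sizeable share of the cohort is exposed, or that the trial's operating characteristics suffer: alpha, power, sample size and the Simon two-stage rule are unaffected.

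**What to change.** Two changes to section 3.4.2:

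1. In the Grade 2 AST/ALT row of Table 14, for an event that has resolved: *restart at the dose the patient was receiving before the hold*.
2. Add one sentence: *no patient is re-escalated above the assigned or already reduced dose*.

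With these, a patient reduced to 12.0 restarts at 12.0, one reduced to 8.0 restarts at 8.0, one assigned 8.0 restarts at 8.0, and patients on DL 0 are treated as now.

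No new sentence on stopping at DL -1 is needed, because the floor rule already covers patients reduced to that level. A blanket rule that also took in patients assigned to DL -1 would remove the step from 12.0 to 8.0 that Table 13 can be read to allow a patient who starts at 12.0. Whether that step is available is for the sponsor to decide.

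The cost is one table cell and one sentence in the next amendment, with no extra patients or procedures.
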